5.5. Withdrawal of Subjects From Study Treatment

5.5.1. Withdrawal Criteria

A subject may choose to withdraw from the study treatment at any time or be withdrawn from the study treatment by the investigator or sponsor if the subject is noncompliant with the study requirements. If a subject is withdrawn from study treatment, then every reasonable effort should be made to determine the reason for withdrawal, and this information should be recorded in the eCRF.

Subjects **must** be withdrawn from **study treatment** for the following reasons:

- The subject becomes pregnant.
- Consent is withdrawn. Subjects may choose to withdraw from the study at any time without penalty of jeopardizing their healthcare or loss of benefits to which the subject is otherwise entitled.
Note: Consent withdrawn means that the subject can no longer be followed and no additional data can be collected. Subjects may choose to discontinue study treatment and remain in the study to be followed for progression and survival.
- Further participation would be injurious to the subject's health or well-being, in the investigator's medical judgment.
- Unacceptable toxicity (see [Section 5.4](#)) occurs. Subjects with unacceptable toxicities must be withdrawn from study treatment but will continue in the follow-up phase of the study (see [Section 6.4](#)).
- The study is terminated by the sponsor.
- The study is terminated by the local health authority, IRB, or IEC.

A subject **may** be discontinued from **study treatment** as follows:

- Confirmed radiographic progression of disease per RECIST v1.1. A subject may be granted an exception to continue on treatment with confirmed radiographic progression if clinically stable or clinically improved (see [Section 7.7.1](#)).
Note: For unconfirmed progression, see [Section 7.7.1](#).
- If, during the course of the study, a subject is found not to have met eligibility criteria (see [Section 3](#)), the medical monitor, in collaboration with the investigator, will determine whether the subject should be withdrawn from study treatment.
- If a subject is lost to follow-up or noncompliant with study procedures or study treatment in the investigator's opinion, the sponsor should be consulted for instruction on handling the subject.

5.5.2. Withdrawal Procedures

In the event that the decision is made to permanently discontinue the study treatment, the subject will be withdrawn, and the EOT visit should be conducted. Reasonable efforts should be made to have the subject return for all applicable follow-up visits (safety and efficacy; see [Section 6.4](#)). The last date of the last dose of study treatment and the reason for subject withdrawal will be recorded in the eCRF.

If a subject is withdrawn from the study treatment:

- The study monitor or sponsor must be notified.
- The reason(s) for withdrawal from treatment must be documented in the subject's medical record and in the eCRF.

Note: The reason for withdrawal from treatment may be different than the reason for withdrawal from study. For example, subjects can discontinue treatment for disease progression or toxicity but remain in the study for safety and survival follow-up.

- The EOT visit should be performed.
- The date of the EOT visit should be recorded in the eCRF and the IRT system.
- Subjects must be followed for safety until the time of the follow-up visit or until study treatment-related toxicities resolve, return to baseline, or are deemed irreversible, whichever is longest.
- Subjects who discontinue for reasons other than disease progression will continue to be followed for disease status as outlined in [Section 6.4.2](#).
- All subjects who discontinue study treatment will continue to be followed for survival as outlined in [Section 6.4.3](#).

If the subject discontinues study treatment and actively withdraws consent for collection of follow-up data (safety follow-up, disease assessments, or survival follow-up), then no additional data collection should occur; however, **subjects will have the option of withdrawing consent for study treatment but continuing in the follow-up period of the study for safety, efficacy, and survival assessments.**

5.6. Concomitant Medications

All concomitant medications and treatments must be recorded in the eCRF. Any prior medication received up to 28 days before the first dose of study treatment and 60 days after the last dose of study treatment or until the subject begins a new anticancer therapy, whichever occurs first, will be recorded in the eCRF. Any addition, deletion, or change in the dose of these medications will also be recorded. Concomitant treatments/procedures that are required to manage a subject's medical condition during the study will also be recorded in the eCRF.

5.6.1. Permitted Medications

All treatments that the investigator considers necessary for a subject's welfare may be administered at the discretion of the investigator in keeping with the community standards of medical care. All concomitant medications will be recorded in the eCRF, including all

prescription and over-the-counter medications, herbal supplements, and IV medications and fluids. If changes occur during the study period, documentation of drug regimen, frequency, route, and date may also be included in the eCRF. **Note:** The use of bisphosphonates and denosumab are permitted in this study.

5.6.2. Restricted Medications

- Systemic glucocorticoids for any purpose other than prophylaxis for contrast allergies for radiographic procedures, to modulate symptoms, or to treat an AE of suspected immunologic etiology are restricted and require medical monitor approval. The use of physiologic corticosteroid replacement therapy may be approved after consultation with the medical monitor.

Note: Inhaled and topical steroids are allowed. A short course of steroids (eg, prednisone or equivalent) at doses ≤ 10 mg/day may be permitted with medical monitor approval.

- Use of the anticonvulsant carbamazepine (a UGT1A9 inducer) is discouraged. Because there is a potential interaction that could result in lower epacadostat exposures, an alternative to carbamazepine should be used, if possible.
- Use of coumarin-based anticoagulants (eg, warfarin) with epacadostat is discouraged. Low-dose warfarin (1 mg) is acceptable; however, other higher doses are discouraged. If an alternative to coumarin-based anticoagulants cannot be used, the INR should be monitored closely per standards of care when epacadostat is started.

5.6.3. Prohibited Medications

Medications or vaccinations specifically prohibited in the exclusion criteria (see [Section 3.2](#)) are not allowed during the study. If there is a clinical indication for one of these medications or vaccinations specifically prohibited during the study, discontinuation from study treatment may be required. The investigator should discuss any questions regarding this with the medical monitor. The final decision on any supportive therapy or vaccination rests with the investigator and/or the subject's primary physician. However, the decision to continue the subject on study treatment requires the mutual agreement of the investigator, the sponsor, and the subject.

Subjects are prohibited from receiving the following therapies during the screening and treatment periods of this study, unless otherwise indicated:

- Any anticancer medications, including chemotherapy or biologic therapy other than study treatment.
- Any immunological-based treatment for any reason from screening through the safety follow-up visit is prohibited.

Note: Completed adjuvant therapy (eg, vaccines) with medical monitor approval, inhaled or topical steroids, systemic steroids (eg, prednisone or equivalents) at doses ≤ 10 mg/day, and immune suppressants are allowed for treatment for irAEs as described in [Section 5.4.7](#) and [Appendix B](#), or as prophylaxis for contrast allergy for imaging procedures.

Note: Allergy shots may be permitted after consultation with the medical monitor.

- Investigational agents other than study treatment. Use of such medications from screening through the safety follow-up visit is prohibited.
- Concomitant radiation therapy.

Note: Radiation therapy to a symptomatic solitary lesion or to the brain may be considered on an exceptional case-by-case basis after consultation with the medical monitor. The subject must have clear measurable disease outside of the radiated field. Administration of palliative radiation therapy will be considered clinical progression for the purposes of determining PFS.

- Live vaccines within 30 days before the first dose of study treatment and while participating in the study. Examples of live vaccines include, but are not limited to, the following: measles, mumps, rubella, chicken pox, yellow fever, rabies, Bacillus Calmette-Guérin, and typhoid (oral) vaccine. Seasonal influenza vaccines for injection are generally killed virus vaccines and are allowed. However, intranasal influenza vaccines are live attenuated vaccines and are not allowed.
- For cohorts where subjects receive epacadostat, use of any melatonin supplements.
- For cohorts where subjects receive epacadostat, use of any MAOI or drug associated with significant MAOI activity agents is prohibited from 21 days before study Day 1 through 14 days after the final dose of epacadostat has been administered (refer to [Appendix C](#)).
- For cohorts where subjects receive epacadostat, any UGT1A9 inhibitor from screening through the safety follow-up, including acitretin, amitriptyline, androsterone, cyclosporine, dasatinib, diclofenac, diflunisal, efavirenz, erlotinib, estradiol (17-beta), flutamide, gefitinib, gemfibrozil, glycyrrhetic acid glycyrrhizin, imatinib, imipramine, ketoconazole, linoleic acid supplements, mefenamic acid, mycophenolic acid, niflumic acid, nilotinib, phenobarbital, phenylbutazone, phenytoin, probenecid propofol*, quinidine, ritonavir, sorafenib, sulfapyrazone, valproic acid, and verapamil.

Note: Propofol, when used for short-term sedation during surgical/biopsy procedures, is allowed after consultation with the sponsor. The epacadostat dose may be taken on the morning of the procedure and the evening dose held following the procedure. Epacadostat may be resumed the next day.

Subjects who, in the assessment by the investigator, require the use of any of the aforementioned treatments for clinical management should be removed from the study. Subjects may receive other medications that the investigator deems to be medically necessary. The exclusion criteria describe other medications that are prohibited in this study (see [Section 3.2](#)). There are no prohibited therapies during the post-treatment follow-up period.

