4.4. Duration of Treatment and Subject Participation

After signing the ICF, screening assessments may be completed over a period of up to 28 days. Subjects may continue to receive study treatment as long as they are deriving benefit and have not met any of the Protocol-defined criteria for treatment withdrawal (see [Section 5.5](#)), or for up to 24 months from the first dose of study treatment, whichever occurs first. If the subject discontinues study treatment, then the treatment period will end, and the subject will enter the follow-up period (see [Section 6.4](#)), for safety and survival. Study participation, including post-treatment follow-up, is expected to average approximately 12 to 18 months per individual subject.

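### Protocol Section 5.6.3 states four bans that expressly run past the last dose, then closes with an unqualified sentence that contradicts them: a minor safety-wording error

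*Protocol*

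**What the plan says.** Section 5.6.3 of the protocol introduces its list with a default window: "Subjects are prohibited from receiving the following therapies during the screening and treatment periods of this study, unless otherwise indicated". Eight entries follow, and four of them set a later end of their own:

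- MAOIs and drugs with significant MAOI activity: use "is prohibited from 21 days before study Day 1 through 14 days after the final dose of epacadostat has been administered".
- UGT1A9 inhibitors: the ban covers "any UGT1A9 inhibitor from screening through the safety follow-up". Exclusion criterion 19 in Section 3.2 repeats this window.
- Immunological-based treatment: "Any immunological-based treatment for any reason from screening through the safety follow-up visit is prohibited".
- Other investigational agents: "Use of such medications from screening through the safety follow-up visit is prohibited".

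A fifth entry has no dated end but may also run on: "Live vaccines within 30 days before the first dose of study treatment and while participating in the study". The remaining three (other anticancer medication, concomitant radiation, melatonin) state no window after the last dose.

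The section's last sentence is "There are no prohibited therapies during the post-treatment follow-up period". It carries no exception and no cross-reference.

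Section 4.4 fixes when follow-up starts: "If the subject discontinues study treatment, then the treatment period will end, and the subject will enter the follow-up period". It adds that this follow-up is for safety and survival.

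**The concern.** One section gives two incompatible instructions for the same weeks. The entry that matters most is the one on MAOIs. Sections 1.3.2 and 5.4.9 present that ban as a precaution against serotonin syndrome, and Section 5.6.3 deliberately extends it beyond the last epacadostat dose. A site relying on the closing sentence could cite written protocol text for dropping the extension as soon as treatment ends, and for dropping the other three bans throughout safety follow-up.

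The documents give no figure for the risk of an MAOI started soon after the last dose, so none is claimed here. Section 1.3.2 reports 2 subjects with serotonin syndrome or its symptoms among 958 treated across the epacadostat program, both mild and resolved.

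**Working it through.** This is a comparison of texts with a little date arithmetic. No power or error-rate figure is involved.

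**1. Count the entries in Section 5.6.3.**

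| Entry | Stated end of ban | Runs past the last dose? |
|---|---|---|
| MAOIs | 14 days after final epacadostat dose | Yes, expressly |
| UGT1A9 inhibitors | Safety follow-up | Yes, expressly |
| Immunological-based treatment | Safety follow-up visit | Yes, expressly |
| Other investigational agents | Safety follow-up visit | Yes, expressly |
| Live vaccines | End of study participation | By inference |
| Anticancer medication, radiation, melatonin | None stated, so the default window applies | No |

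That is 4 express + 1 inferred + 3 without extension = 8 entries. The inference for live vaccines rests on Section 4.4, which counts post-treatment follow-up as part of study participation.

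**2. Does the post-treatment period include safety follow-up?** Three places say so. Section 4.4 has the subject enter follow-up, for safety among other purposes, when treatment stops. Section 6.4 lists safety follow-up first among its three kinds of follow-up. Table 11 sets both safety visits under its post-treatment heading.

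**3. Does the qualifier in the lead-in resolve the conflict?** It lets an entry depart from the default screening-and-treatment window. It is attached to the list. The closing sentence comes after the list and has no qualifier.

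**4. Length of the MAOI conflict.** Let d be the days from the last epacadostat dose to the end of the treatment period. Section 6.2 ends that period when the investigator decides on permanent discontinuation. The conflict lasts max(0, 14 − d) days:

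- d = 0: 14 days, the protocol's own figure
- d = 7: 7 days
- d = 10: 4 days
- d = 14: 0 days
- d = 28: 0 days

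The case d = 28 can occur because Section 5.4.6 allows treatment to be held for up to 28 days for toxicity.

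**5. Length of the conflict for the other three bans.** The protocol times the safety visits from two different anchors.

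- Section 6.4.1 counts from the end-of-treatment (EOT) visit. The second visit falls at 60 to 60 + 7 = day 60 to 67 after EOT.
- Table 11, footnote b, counts from the last dose of study treatment. With the same +7 window, the second visit falls at day 60 to 67 after that dose. Measured from the end of the treatment period, and with d now counted from the last dose of any study treatment, the conflict is 60 − d to 67 − d days. That is 60 to 67 days at d = 0, and 60 − 28 = 32 to 67 − 28 = 39 days at d = 28.

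Under either anchor it is shorter if the visit is brought forward ahead of a new anticancer therapy, as Section 6.4.1 and footnote b provide.

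**6. Which safety visit?** Two entries refer to a single visit, although there are two, at 30 (+7) and 60 (+7) days. Section 6.4.1 itself uses the singular for both. Sections 5.6 and 8.1.2 carry concomitant-medication recording and AE monitoring to 60 days unless a new anticancer therapy starts first. The second visit is therefore the natural end, and step 5 uses it.

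**The case against.** The best defence is that ordinary reading settles the matter. A specific, dated ban normally prevails over a general closing remark, and the lead-in allows entries to set their own windows. Other text sides with the entries: Sections 1.3.2 and 5.4.9 bar MAOIs for the duration of the study, and exclusion criterion 19 repeats the UGT1A9 window. Much of this stands. A careful site would probably keep to the entries, and the medical monitor is available for questions. But the protocol states no rule of precedence, and a safety instruction should not depend on one being supplied.

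A second defence is that post-treatment follow-up is not a defined term and could mean only disease-status and survival follow-up, when new anticancer therapy is expected. That reading would remove most of the conflict. Section 4.4 and Table 11 point the other way, and nothing in the protocol adopts it.

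A reader might also infer more than the documents support:

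- **That the protocol authorizes MAOIs straight after the last dose.** No passage says so. It follows only from taking one sentence in isolation.
- **That every subject has a 14-day gap.** Fourteen days is the maximum, and the gap can be zero.
- **That five bans are plainly contradicted.** Four are. Live vaccines join them only through Section 4.4.
- **That the end of two bans is uncertain by about a month because the visit is not named.** Sections 5.6, 6.4.1 and 8.1.2 largely settle it at 60 days.

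**Conclusion.** The contradiction is in the current text and owes nothing to redaction. The closing sentence of Section 5.6.3 is wrong as written against four express bans, and arguably a fifth. Read literally, it removes the MAOI safeguard for 0 to 14 days and the other three bans until about 60 (+7) days after EOT (Section 6.4.1) or after the last dose (Table 11, footnote b).

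These lengths assume that the second safety visit ends the three bans, that no new anticancer therapy brings that visit forward, and that the EOT visit falls on the day the treatment period ends (Table 11 allows ±3 days).

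This is a minor correction to safety wording, with no bearing on any endpoint or analysis. Its reach is also small. SAP Sections 9 and 10.1.1.2 record that enrollment stopped, with a limited number of subjects in Group C and none in Groups B or D. Treatment may last up to 24 months (Section 4.4), and the SAP does not say how many subjects were still on treatment.

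**What to change.** 1. Open the closing sentence of Section 5.6.3 with an exception, leaving the rest as it stands: *Except where a longer prohibition is stated above (MAOIs, UGT1A9 inhibitors, immunological-based treatment, investigational agents), …*
2. Give the live-vaccine ban an explicit end, for example the 60-day safety follow-up visit. Adding live vaccines to the exception without an end date would confirm a ban through survival follow-up, by which time Section 7.4 no longer requires concomitant medications to be recorded.
3. Optionally, name the 60-day visit in the immunological-treatment and investigational-agent entries.

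The cost is one clause and one end date, plus a named visit in two entries if item 3 is taken up. A clarification note to sites suffices. No visits, subjects or analyses are added.

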6. STUDY ASSESSMENTS

All study assessments will be performed as indicated in the schedule of clinical assessments ([Table 11](#)), and all laboratory assessments will be performed as indicated in [Table 12](#). [Table 13](#) presents a summary of clinical laboratory analytes to be assessed. The order of assessments is suggested by the order of mention within the schedule. See [Section 7](#) for instructions on each assessment. Further details of study procedures and assessments can be found in the Study Reference Manual or applicable procedural documentation.

Table 11: Schedule of Assessments

Visit Day (Range)	Protocol Section	Screening	Treatment ^a						Post-Treatment ^b			
			Cycles 1 and 6			Cycle 2	All Other Cycles	Every 9 Weeks	EOT	Safety Follow-Up Visit 1	Safety Follow-Up Visit 2	Survival Follow-Up
			D1	D8	D15	D1	D1	Disease Status				Every 12 weeks
Evaluation/Window		Days -28 to -1		± 1 day	± 3 days	± 3 days	± 3 days	± 7 days	± 3 days	30 days (+ 7 days)	60 days (+ 7 days)	± 7 days
Informed consent	7.1	X										
Inclusion/exclusion criteria	3.1, 3.2	X	X ^c									
Contact IRT	7.2	X	X			X	X		X			
Medical and cancer history	7.3.1, 7.3.2	X										
Prior/concomitant medications	7.4	X	X	X	X	X	X		X	X	X	
Administer INCAGN01876	5.2.1.1		X			X	X					
Administer pembrolizumab	5.2.3.1		X ^d			X	X					
Administer/dispense epacadostat at site	5.2.2.1		X ^e			X ^e	X ^e					
Poststudy anticancer therapy status	7.5									X	X	X
Survival status	6.4.3											X
Comprehensive physical examination (including height)	7.6.2.1	X										
Targeted physical examination	7.6.2.2		X	X ^f	X ^f	X	X		X	X	X	
Vital signs and weight	7.6.3	X	X	X ^f	X ^f	X	X		X	X	X	
ECOG performance status	7.8.1	X	X	X ^f	X ^f	X	X		X	X	X	
Laboratory assessments	7.6.5	X	X	X	X	X	X		X	X	X	
12-Lead ECG ^g	7.6.4	X	X ^h			X ^h			X	X		
AE assessment	7.6.1	X	X	X ^f	X ^f	X	X		X	X	X	
Distribute subject reminder cards	7.11.1		X	X	X	X	X		X	X		
Radiologic tumor assessments	6.4.2, 7.7	X ⁱ						X ^j	X ^k	X ^l		

[figure not shown]
^a Treatment cycles will be every 3 weeks (21 ± 3 days).

[figure not shown]
^b The mandatory safety follow-up visits should be conducted approximately 30 days and 60 days after the last dose of study treatment or before the initiation of a new anticancer treatment, whichever comes first.

- ^c Screening laboratory tests performed more than 7 days before Cycle 1 Day 1 must be repeated and eligibility confirmed before study treatment administration on Cycle 1 Day 1.
- ^d In Treatment Groups B and D, pembrolizumab administration begins at Cycle 2 Day 1.
- ^e Epacadostat is only required to be dosed at the site on Day 1 of Cycle 1 and Cycle 2.
- ^f Only required for Cycle 6 Day 8 and Cycle 6 Day 15 if the subject is experiencing an AE > Grade 2.
- ^g All 12-lead ECGs will be performed at the study site with the subject in a recumbent or semirecumbent position after 5 minutes of rest and should not be performed within 15 minutes after a blood sample collection.
- ^h A 12-lead ECG will be collected before the morning dose of epacadostat on Cycle 1 Day 1 and Cycle 2 Day 1, and 2 hours (\pm 15 minutes) after the morning dose of epacadostat on Cycle 1 Day 1 and Cycle 2 Day 1 (see [Table 14](#)).
- ⁱ The initial tumor imaging will be performed within 28 days before the first dose of study treatment. Scans performed as part of routine clinical management are acceptable for use as the screening scan if they are of diagnostic quality and performed within 28 days before the first dose of study treatment. The same imaging technique should be used for a subject throughout the study. Local reading (investigator assessment with site radiology reading) will be used to determine eligibility and for subject management.
- ^j On-study imaging will be at Week 9 and then every 9 weeks (\pm 7 days) for the first 12 months and then every 12 weeks (\pm 7 days) thereafter. Imaging should follow calendar days and should NOT be adjusted for delays in cycle starts. If imaging shows disease progression, then another imaging assessment should be performed at a minimum of 4 weeks, but no more than 6 weeks, later to confirm disease progression per mRECIST.
- ^k If a scan was obtained within 4 weeks prior to the date of treatment discontinuation, then a scan at treatment discontinuation (EOT) is not mandatory. For subjects who discontinue study therapy without confirmed disease progression, a radiologic evaluation should be repeated at the time of treatment discontinuation (ie, date of discontinuation \pm 4 week window).
- ^l For subjects who discontinue treatment for a reason other than disease progression (eg, toxicity), every effort should be made to collect information regarding disease status every 9 weeks (\pm 7 days) for 12 months and then every 12 weeks (\pm 7 days) thereafter by radiographic imaging until 1) the start of new anticancer therapy, 2) documented disease progression, 3) death, 4) the end of the study, or 5) withdrawal of consent, whichever occurs first.

Table 12: Schedule of Laboratory Assessments

Visit Day (Range)	Protocol Section	Timing of Assessment	Screening Days -28 to -1	Treatment										Post-Treatment			
				C1			C2	C4	C6			C7	C8 and Every 4th Cycle	All Other Cycles	EOT	Safety Follow-Up Visit 1 30 days (+ 7 days)	Safety Follow-Up Visit 2 60 days (+ 7 days)
				D1	D8	D15	D1	D1	D1	D8	D15	D1	D1	D1			
Evaluation/Window				Predose	± 1 day	± 1 day	± 3 days	± 3 days	± 3 days	± 1 day	± 1 day	± 3 days	± 3 days	± 3 days	± 3 days		
Local laboratory tests^a																	
Comprehensive serum chemistries ^b	7.6.5	N/A	X ^c	X ^d	X	X	X	X	X			X	X	X	X	X	X
Hematology with differential	7.6.5	N/A	X ^c	X ^d	X	X	X	X	X			X	X	X	X	X	X
Coagulation panel ^e	7.6.5	N/A	X ^c														
Urinalysis	7.6.5	N/A	X ^c												X		
Endocrine function tests	7.6.5	N/A	X ^c				X					X		X	X		
HBV and HCV tests	7.6.5.2	N/A	X														
Serum pregnancy test (childbearing females only) ^f	7.6.5.1	N/A	X											X			
Urine pregnancy test (childbearing females only)	7.6.5.1	N/A		X ^g													

All safety laboratory assessments will be performed locally.

- ^b If liver chemistry tests are abnormal (eg, change in grade from baseline), then liver chemistry monitoring should increase to once per week until resolved to baseline or \leq Grade 1. Liver chemistry does not need to be monitored once per week indefinitely for persistent low grade abnormalities. Appropriate liver chemistry monitoring intervals should be discussed with the medical monitor for these circumstances.
- ^c Screening laboratory tests must be performed within 7 days of Cycle 1 Day 1. If performed more than 7 days before Cycle 1 Day 1, then the tests must be repeated and eligibility confirmed before study treatment administration on Cycle 1 Day 1.
- ^d Only required to be performed at Cycle 1 Day 1 if the screening assessment was not performed within 7 days prior.
- ^e Subjects on anticoagulation treatment should have parameters monitored throughout the study as clinically indicated.
- ^f A serum pregnancy test will be required for all females of childbearing potential during screening and at EOT. The serum pregnancy test performed at screening must be performed within 72 hours before the first dose of study treatment.
- ^g Urine pregnancy tests will be performed locally as clinically indicated or per country-specific requirements (see [Section 7.6.5.1](#)).

[figure not shown]

Table 13: Local Laboratory Tests: Required Analytes

Serum Chemistries	Hematology	Urinalysis	Hepatitis Screening	Coagulation
Albumin Alkaline phosphatase ALT AST Bicarbonate Blood urea nitrogen Calcium Chloride Creatinine Glucose Lactate dehydrogenase Phosphate Potassium Sodium Total bilirubin Direct bilirubin (if total bilirubin is elevated above ULN) Total protein Uric acid Amylase Lipase	Complete blood count, including: 
 • Hemoglobin • Hematocrit • Platelet count • Red blood cell count • White blood cell count Absolute values must be provided for WBC differential laboratory results: 
 • Basophils • Eosinophils • Lymphocytes • Monocytes • Neutrophils 	Color and appearance pH and specific gravity Bilirubin Glucose Ketones Leukocytes Nitrite Occult blood Protein	HBV surface antigen HBV core antibody HBV-DNA HCV antibody HCV-RNA	PT aPTT INR
			Pregnancy Testing	Endocrine Monitoring
			Female subjects of childbearing potential only require a serum test at screening and at EOT. Urine pregnancy tests should be repeated if required by local regulations.	Thyroid-stimulating hormone (TSH) Free thyroxine (T4) Total triiodothyronine (T3)/FT3 ^a

^a If considered standard by your region.

